34. Principal Investigator's Assurance	22
35. CHECKLIST SECTION.....	24
36. Partial Waiver of Consent for Screening/Recruitment.....	24
37. Partial Waiver of HIPAA Authorization for Screening/Recruitment.....	25
38. Waiver of Documentation of Consent	25
39. Alteration of Consent.....	26
40. Full Waiver of Consent/Parental Permission	27
41. Full Waiver of Consent/Parental Permission (Public Benefit or Service Programs)	28
42. Full Waiver of HIPAA Authorization (Checklist)	28
43. Other Waiver Types (Checklist).....	29

PROTOCOL TITLE: **Improving Healthcare Outcomes in American Indian and Hispanic Transplant Recipients Using Culturally-Tailored Novel Technology (IMPACT)**

44. Vulnerable Populations (Checklist).....	29
45. Medical Devices (Checklist).....	35
46. Export Control (Checklist)	36
47. Data Transfer/Sharing (Checklist)	36
48. Specimen Transfer/Sharing (Checklist).....	37

PROTOCOL TITLE: **Improving Healthcare Outcomes in American Indian and Hispanic Transplant Recipients Using Culturally-Tailored Novel Technology (IMPACT)**

1. Objectives

Aim 1: Examine IMPACT's acceptability and feasibility in AI and HL KT recipients.

1a. We will assess acceptability by patient ratings of satisfaction with the culturally-tailored diet and exercise intervention, as well as the Twistle patient engagement platform.

1b. We will assess feasibility by determining recruitment and retention rates and assessing participant adherence to the IMPACT intervention.

1c. We will determine the ideal personnel hours and number of staff required for the physical therapist/exercise physiologist and registered dietitian nutritionist roles.

Aim 2: Test the efficacy of IMPACT on proximal outcomes (e.g., weight, lipid profile, HbA1c, sleep quality, QOL) and distal outcomes (e.g., occupational functioning) in kidney transplant recipients.

2a. We will assess participants' adherence to the exercise and diet intervention aspects of IMPACT.

2b. We will begin to examine the relationship between adherence to IMPACT and patient outcomes.

2. Background

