with Twistle will be used by those with or without a smartphone, and addresses recent

PROTOCOL TITLE: **Improving Healthcare Outcomes in American Indian and Hispanic Transplant Recipients Using Culturally-Tailored Novel Technology (IMPACT)**

and ongoing concerns regarding broadband internet and provider access in rural communities.^{48,49}

For our research purposes, we will use Twistle to create and deploy our participant questionnaires because it is compatible with RedCap. We will also use it to send personalized reminders and check-in with participants based on the culturally-tailored exercise and diet plan developed by our intervention team to assess and maintain adherence to the intervention. Twistle also enables the data to be pushed to a reimbursement database, so that our research team is triggered to provide participant payments. Finally, we will use Twistle to track participant status throughout the research protocol. The application will allow us to confirm message delivery, patient engagement, and monitor triage alerts.

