We will randomly assign participants to either the IMPACT intervention of usual care (UC) prior to their first intervention point. [name] (lead statistician) will develop a random allocation scheme by considering stratification to form blocks with respect to important determinants such as ethnicity, gender, etc. Within each stratum or block, we will accomplish random allocation to IMPACT vs UC with systematic sampling (e.g. alternating the assignment of IMPACT and UC with a random start). This scheme will result in a nearly equal number of patients in IMPACT and UC within a block. We will reduce potential bias using stratified randomization by preventing potentially inferring treatment allocation *a priori*. It also reduces bias by balanced assignment so that potential determinants of outcomes are comparable across intervention groups. We can also use systematic sampling to reduce sampling variation in comparison with simple random sampling. Because of the close interaction between the clinical team and the research interventionists, we will not be able to blind the clinical team to group assignment.^{50,51} After [name] creates the allocation scheme, he will give it to the research coordinator, who will put the allocation assignments into separate sealed envelopes. The research coordinator will place the master list in a locked file cabinet drawer in the office of the PI's Office Administrator. Only the sequence numbers (A1 – block A patient #1, A2, A3, etc.) will appear on the sealed envelopes and the corresponding group assignment will be placed inside the envelope. The research coordinator will open the sealed envelope sequentially and inform the consented participant of his or her assigned group. After random assignment, the research coordinator will direct participants in the IMPACT intervention to the study interventionists (the physical therapist and dietitian).

4. Inclusion and Exclusion Criteria

We plan to recruit participants shortly before or after undergoing KT at the UNM HSC Transplant Center. The Transplant Center provides transplant services to all New Mexico residents as well as the surrounding Pueblos and the Navajo Nation. Reflecting the demographics of the state, only 3% of patients are AA at UNM. Male and female KT recipients aged 18 and older will be eligible for enrollment.

Transplant Patients

Inclusion criteria:

1. Received kidney transplant at the University of New Mexico
2. Greater than 18 years of age

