PROTOCOL TITLE: **Improving Healthcare Outcomes in American Indian and Hispanic Transplant Recipients Using Culturally-Tailored Novel Technology (IMPACT)**

3. American Indian (AI) or other race, White (WH) or Hispanic/Latina(o) (HL)
4. Mentally competent

Exclusion criteria:

1. Children under the age of 18
2. Incarcerated patients
3. Pregnant women

Team Members

Inclusion criteria:

1. Transplant clinic staff
2. Key administrators involved in the transplant process

5. Number of Subjects

To estimate the number of patients we can expect to recruit for the study, we used data from the last five years of KT recipients at UNM HSC. The center transplants an average of 33 patients per year. For the study, we plan a 12-month recruitment period. Of all eligible patients who receive a KT, we expect that 80% will agree to participate in our study (n=26), based on previous intervention research with KT patients,^{13,16,17,34,41,52-54} and our own work.⁵⁵⁻⁵⁷ Thus, for this pilot trial, we aim to recruit and retain 14-20 KT recipients. Virtually all of UNM ESKD patients are (a) HL (44%) or AI (33%), (b) income <\$25K, (c) on public insurance, (d) high school or lower education; and/or, (e) low occupational status. Thus, our patient sample will include members of different vulnerable populations that have been underrepresented in past research, and hence prepare us to conduct a formal study in a diverse population.

Team members will include up to fifteen people from the following groups: transplant clinic staff and key administrators.

6. Study Timelines

Participant expected duration in the study will be one year, if they complete all study visits. Patient recruitment and enrollment will be completed in 12 months of the study (Month 4, Year 1 through Month 3, Year 2). Participant follow-up, data analysis, and manuscripts are schedule to be completed in Year 2 of the study.

Project Period: 03/01/2020 – 02/28/2022									
Activity	Year: Month:	01		02					
		1-3	4-6	7-9	10-12	1-3	4-6	7-9	10-12
Project Startup (e.g., hiring and training staff; database creation)		----							
Participant Recruitment		-----		---					

PROTOCOL TITLE: **Improving Healthcare Outcomes in American Indian and Hispanic Transplant Recipients Using Culturally-Tailored Novel Technology (IMPACT)**

Participant Follow-up		
Team Member Surveys		
Data Quality Evaluation and Observation Logging	-----	-----
Data Analysis		-----
Present Initial Findings at Conferences		---

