Subjects are free to withdraw from study participation at any time during this clinical study. The Investigator may withdraw a subject if continued participation is not in the interest of the subject's health and welfare, for noncompliance with protocol-specified procedures, or because of a protocol violation. This will be evaluated on a case-by-case basis by the Investigator. All data collected from a withdrawn participant will be destroyed if the participant withdraws from the study at any point.

The primary reason for discontinuation or withdrawal will be documented as one of the following:

- Adverse Event
- Noncompliance
- Protocol violation

16. Data Management/Confidentiality

The PI will oversee all aspects of data management in close collaboration with the lead study statistician, [name]. The study team will work with the Twistle, Inc. team to develop an operations manual to standardize all procedures and staff training in areas such as patient recruitment, measurement, assessment, and data entry, management, and security. Following the guidelines outlined in the operations manual the statistical team will create an electronic data entry system using REDCap,

PROTOCOL TITLE: Improving Healthcare Outcomes in American Indian and Hispanic Transplant Recipients Using Culturally-Tailored Novel Technology (IMPACT)

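### Section 15 orders all data from a withdrawn participant destroyed, so adherence data already collected from formal withdrawers drop out of the Aim 1b feasibility estimate

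*Combined protocol and SAP*

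**What the plan says.** Section 15 allows participants to leave at any time and lets the investigator withdraw a participant on welfare grounds, for noncompliance or for a protocol violation. It then states: "All data collected from a withdrawn participant will be destroyed if the participant withdraws from the study at any point". It also requires the main reason for withdrawal to be documented.

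Other sections rely on data that this rule would remove:

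- **Section 1, Aim 1b:** "We will assess feasibility by determining recruitment and retention rates and assessing participant adherence to the IMPACT intervention".
- **Section 1, Aim 2b:** "We will begin to examine the relationship between adherence to IMPACT and patient outcomes".
- **Section 3:** Twistle reminders and check-ins follow the exercise and diet plan "developed by our intervention team to assess and maintain adherence to the intervention", so adherence is assessed while participation is under way.
- **Section 7:** feasibility is a primary endpoint. The same paragraph plans a between-arm comparison of activity-monitor data and seeks estimates of missing-data and attrition rates.
- **Section 13:** the primary analysis covers the Aim 1 measures. Missing data, attrition and its reasons are to be summarised. The Aim 1 and Aim 2 analyses support the go/no-go decision.
- **Section 14:** the independent reviewer is to see all data captured for the study.

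The weekly archives in Section 16 are routine backups, erased after one year. They do not keep a withdrawn participant's data for analysis.

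**The concern.** In a feasibility pilot, the people who withdraw are among the most informative. Someone who leaves partway may already have given a baseline interview, activity-monitor records and adherence responses. Read literally, Section 15 destroys all of these. The gap is made by the rule, not by the participant's departure, and no analysis can repair it afterwards.

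The adherence figure for Aim 1b would then exclude formal withdrawers. If they adhered less than the others, the figure passed to the next study and to the go/no-go decision would be too favourable. The rule also turns observations that were collected into missing ones, although the pilot is meant to measure how much data go missing.

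The scope of the rule is unclear as well. It speaks of a withdrawn participant but adds a condition about the participant withdrawing. It is therefore uncertain whether data are destroyed when the investigator withdraws someone, for example for noncompliance.

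**Working it through.** **1. The plan's own figure.** Section 5 gives 33 transplants a year, 12 months of recruitment and 80% agreement: 33 × 0.80 = 26.4. The plan states 26 ("we expect that 80% will agree to participate in our study (n=26"), so the figure reproduces. The target is smaller: "for this pilot trial, we aim to recruit and retain 14-20 KT recipients".

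**2. Arm sizes.** Section 3 says of the allocation: "This scheme will result in a nearly equal number of patients in IMPACT and UC within a block". With two roughly equal arms, 14/2 = 7, 20/2 = 10 and, if all 26 are randomised, 26/2 = 13.

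**3. Share of an arm lost, and error in the adherence proportion.** Let n be the number in the IMPACT arm and k the number who formally withdraw. Let p_N be the adherence proportion among those who do not withdraw and p_W the proportion among withdrawers.

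- Share lost = k/n.
- Estimate after destruction = p_N.
- Estimate with data kept = [(n − k) p_N + k p_W]/n.
- Overstatement = (k/n)(p_N − p_W).

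The plan gives neither k nor the gap p_N − p_W. The values k = 1 and 2, and gaps of 0, 25 and 50 percentage points, are assumptions.

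| n | share lost, k=1 | share lost, k=2 | k=1, gap 25 | k=1, gap 50 | k=2, gap 50 |
|---|---|---|---|---|---|
| 7 | 14.3% | 28.6% | 3.6 | 7.1 | 14.3 |
| 10 | 10.0% | 20.0% | 2.5 | 5.0 | 10.0 |
| 13 | 7.7% | 15.4% | 1.9 | 3.8 | 7.7 |

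The last three columns are percentage points. With a gap of 0 the overstatement is 0 in every row.

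**4. What the rule removes and what would be missing anyway.** Section 12 schedules four activity-monitor periods: after stabilisation, near the end of rehabilitation, at 6 months and at 12 months. Any of them may be delayed.

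- *Withdrawal before 6 months.* The 6- and 12-month assessments are missing under any rule. The rule removes the baseline data, adherence responses so far and up to 2 of the 4 monitor periods. This affects Aim 1b. Aim 2b loses little because of the rule.
- *Withdrawal between 6 and 12 months.* The rule also removes the completed 6-month assessment, so both adherence and a follow-up outcome are lost. This is where Aim 2b is affected.

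**5. What could survive.** Section 3 says "we will use Twistle to track participant status throughout the research protocol", the allocation list is held separately, and Section 15 documents the reason for withdrawal. Retention counts and reasons can therefore largely be rebuilt. None of these records is written as exempt from destruction.

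**The case against.** The strongest reply is that the effect is narrow, assumed and small beside sampling noise. Several parts of it stand.

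- **A reader might infer that adherence would describe only those who stay to the end.** The text does not support that. The rule does not mention participants who are lost to follow-up, die or stop adhering without withdrawing, and on its wording their data remain.
- **A reader might infer that the retention rate is lost.** It is not, for the reasons in step 5 of the working.
- **A reader might charge the whole of Aim 2b to the rule.** Anyone leaving before 6 months lacks the later assessments in any case.
- **A reader might count visits.** From Section 12, about 4 weekly visits, 4 fortnightly visits and 3 monthly visits make 11 scheduled dietitian contacts through month 6, of which 8 fall in the first three months. These are scheduled contacts, not adherence measurements. Section 12 lists diet and exercise adherence as a questionnaire measure, and its timing is in Figure 2, which was not available. The same applies to the satisfaction and usability ratings.
- **Precision is poor anyway.** An exact 95% interval for 6 of 7 adherent runs from 42% to 99.6%, and the plan states no adherence threshold for go/no-go. No changed decision can be shown.

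The core point survives. Wide intervals do not justify discarding observations from a very small sample. Visit payments, status tracking and barrier logs do not hold the adherence measures. Reporting unanticipated events within 24 hours (Section 14) covers part of the safety record, but Section 15 still makes no exception for someone who leaves because of an adverse event. The rule may mirror a promise in the consent form, which could not be checked; the fix allows for that.

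**Conclusion.** The point holds for formal withdrawers. As written, Section 15 destroys their adherence, baseline and activity-monitor data, and this conflicts with Aim 1b and with the planned summary of missing data. It should be corrected before any data are destroyed.

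The share lost per withdrawal follows from the plan's own numbers. The bias does not: its direction rests on withdrawers adhering less than the others, and its size on an assumed gap and an assumed count. With one withdrawal and a gap of 0 to 50 points, it lies between 0 and 7.1 points. Confidence is high on what the text says and lower on how much it would change the results. For Aim 2b the conclusion is limited mainly to withdrawals after the 6-month assessment.

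**What to change.** Replace the destruction sentence in Section 15 with wording such as: *Data collected up to withdrawal, by the participant or by the investigator, are retained and analysed in the randomised group; no new data are collected after withdrawal without the participant's agreement; data are destroyed only on the participant's specific request; the fact, date, arm and reason of withdrawal and any adverse events are still recorded.* This also settles whether withdrawal by the investigator is covered.

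Align the consent form with this wording, and honour any promise of destruction already made to participants who have consented.

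The cost is protocol text and possibly a consent amendment, with no extra visits, staff or patients. Reported adherence may look slightly less favourable. As a separate minor matter, the three listed withdrawal reasons include none for a participant's own decision; adding one would help the attrition summary but is not needed for this point.

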Intervention timing: We will minimize participant burden by applying the interventions during patients' standard post-transplant clinic visits. We display how the intervention time points correspond to the standard clinic schedule in Figure 2. The transplant team schedules patients for appointments at the post-transplant clinic 1x/week for the first month, then every two weeks for the next two months, then once a month at 4-6 months post-KT. Surgical clearance usually occurs 6-8 weeks post-KT, at which point the exercise intervention can begin. We will take advantage of these frequent in-person visits to deploy our exercise and diet intervention. Prior to the start of the exercise intervention, we will include a "baseline" test. We will measure time spent sedentary (sitting/lying), standing, and stepping (and the intensity) during awake hours with the activPAL3 accelerometers. At the baseline visit for both groups, we will assess self-reported exercise and physical functioning prior to transplant. Those in usual care will not undergo any diet or exercise intervention, but will wear an activity monitor. They will only undergo the baseline interview, and a follow-up at 6 and 12-months post-transplant. We will repeat the objective assessment of sedentary and physical activities at the 6 and 12-month follow-ups for all participants.

Participants in either arm may have delayed activPal monitor assessments at any of the four timepoints, based on current health status and at the discretion of the PI.

Figure 2. IMPACT and UC Participant Pathway

Exercise intervention: Patient-reported levels of physical activity and objective measures of physical fitness indicate lower levels of exercise in ESKD patients awaiting KT. After KT, physical activity increases, but it remains lower than in the general population.¹²²⁻¹²⁵ Based on the most recent meta-analyses/reviews of physical activity post-transplant,^{33,126,127} our approach combines instructions that are professionally-assessed with the culturally-tailored assessment of exercise needs (Appendix A), guided by a therapist, and incorporate a rehabilitation approach to slowly increasing KT recipients' physical activity⁴⁰⁻⁴² with appropriate build-up to more intense physical activity until they can engage in KDOQI guideline-based exercise.¹²⁸ After the initial

PROTOCOL TITLE: **Improving Healthcare Outcomes in American Indian and Hispanic Transplant Recipients Using Culturally-Tailored Novel Technology (IMPACT)**

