rehabilitation intervention, the latter set of KDOQI guideline-based target activities will include movements that can be performed in the home without supervision or the use of equipment such as abdominal curls, pushups, running in place, vertical jumps, stretching exercises, movement to music, study-provided therapy bands, and some basic yoga exercises. Each at-home session will last about 30-minutes, with the goal of engaging participants in continuous movement.

Participants will be asked to wear the activPAL3, an electronic activity monitor, for the objective assessment of sedentary activity and physical activity. The small, thin device (like a patch) will be worn on their mid-thigh (day and overnight) for 4-7 days after transplant stabilization, at the end of near the end of rehabilitation, at 6 months, and at 12 months. This is not a tracking device. The activity monitor will record general movement (sitting, standing, and stepping) and will enable us to get a better idea of the participant's daily activity and inactivity levels (versus self-report alone). We will also provide participants instructions for applying and removing the monitor. The activPAL3 monitor will be mailed to the study team after each use. After data collection, participants will be given the following instructions:

Once you have completed using the ActivPAL monitor, please remember to return it to our office using the pre-paid mailer we provided. You can drop off the mailer at any post office location. Please contact the study coordinator at [contact] if you have any questions.

Participants will be given safety instructions (see Exercise Instructions) related to at-home exercise, in writing and orally, to help support their physical activity after transplant. The instructions will also be delivered through Twistle for intervention participants.

The study team will follow COVID safe practices as outlined in the related attachment. Additionally, if participants are transitioned to remote clinic visits per the transplant team and therefore not coming in-person to the hospital for their routine appointments in order to minimize COVID exposure, activPal monitors may be mailed. (see attached sample letter)

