Dietary intervention: As in most other KT centers, post-transplant usual care in our transplant center includes one post-transplant visit with the registered dietitian. Patients only see a dietitian again if they return to clinic specifically with a nutritional issue. In contrast, KT recipients in our IMPACT trial will see the dietitian interventionist at every post-transplant appointment through six months post-transplant, with follow-up at 12 months post-txp (Figure 2). Based on dietary and nutritional guidelines from KDOQI and other national and international sources,^{128,129} we plan to have the first nutrition visit (including the culturally-tailored assessment of dietary needs and access, Appendix B) occur immediately after transplant because patients are dealing with a lot of information and instructions post-transplant and may otherwise lose sight of their dietary needs. Thus, recruiting patients and starting the intervention early post-transplant will ensure that they

PROTOCOL TITLE: Improving Healthcare Outcomes in American Indian and Hispanic Transplant Recipients Using Culturally-Tailored Novel Technology (IMPACT**)**

perceive the importance of diet and exercise with the same seriousness as immunosuppression and other aspects of their post-transplant regimen. The continued support they receive from a registered dietitian at the additional follow-up visits will support dietary patterns that meet their individualized nutritional needs post-transplant while also helping to establish behaviors that reduce the risk of excess weight gain and elevated cardiometabolic risk.

Usual care groups: All participants will continue to receive care according to national standards. As required, all patients will have laboratory evaluations 2-3x/per week during the first month post-txp with a clinic visit 1-2x/week. Between months 1 and 3, labs will be drawn weekly or bi-weekly (depending on the stability of the patient), with a clinic visit every 2 weeks. In months 3-6, patients have labs drawn every 2 weeks, or once a month (depending on the stability of the patient), with a monthly clinic visit. Finally, in months 6-12, patients get labs every 1-2 months, and have a monthly clinic visit. However, none of these lab draws will be used for the research study.

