Participant name and other identifying information will be linked to a unique study ID once consented. This study ID will not display any information that can identify the participant. All of the data collected from the participant, including recorded and transcribed interviews, will be coded using participant study ID and the link will be kept in a locked cabinet, and/or password protected computer files. The master list linking participant identifying information to participant study data will be kept in a separate, secure location at UNM. Only the UNM study team will have access to the master list. We will keep the link between participant identifying information and study data until the end of the research study. This link will only be available to UNM, and will not be accessed by researchers at other institutions.

17. Data and Specimen Banking

NA

18. Risks to Subjects

This trial is voluntary and those undergoing KT who do not wish to participate will have access to usual care. We will obtain consent via a formal signed consent form. Patients will be provided adequate time to weigh enrolling in the trial.

The assessors and interventionists will be sure to interview patients in a respectful manner, and will have enough knowledge to be able to explain what steps would be taken to ensure patient confidentiality. For some patients, discussing the intervention and their adherence to it, may be upsetting. Any patients requesting additional counseling will be provided with contact information for the transplant team social

PROTOCOL TITLE: Improving Healthcare Outcomes in American Indian and Hispanic Transplant Recipients Using Culturally-Tailored Novel Technology (IMPACT)

worker. Participants will be reminded that they have the option of discontinuing study participation at any time or taking a break if the interview length feels too burdensome. Results from our current work indicate that the interview should be completed in approximately 30 minutes or less.

We expect the risks associated with the diet and exercise intervention to be minimal because the licensed dietitian and physical therapist on the research team will closely monitor the patient participants, to minimize risk. However, if the patient feels there is an exercise they cannot do, we will urge them to discuss their concerns with the physical therapist.

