We will compensate participants \$20.00 for each completed visit; three visits for participants randomized to usual care and thirteen visits for participants randomized to IMPACT intervention. IMPACT intervention participants will be given an additional \$20 for the in-depth interview at their last follow up visit. The payments will be issued at the completion of each visit in the form of a merchandise card.

24. Compensation for Research-Related Injury

If the subject becomes sick or injured as a direct result from the study, they may receive emergency treatment, however, there is no commitment by the UNM HSC to cover the costs related to research related injuries. The subject and/or their third party payer will be charged in the usual way.

25. Consent Process

We will obtain consent via a formal signed consent form. All potential participants will be given as much time as they need for consent review prior to signing the consent form and will be asked to verbalize the purpose of the study as a check for understanding. The consent form will then be signed and dated by the participant before initiation of any study activity.

Subjects not fluent in English

NA

Cognitively Impaired Adults/Adults Unable to Consent/Use of a Legally Authorized Representative

NA

Subjects who are not yet adults (infants, children, teenagers)

NA

Waiver or Alteration of Consent Process (consent will not be obtained, required element of consent will not be included, or one or more required elements of consent will be altered)

We are requesting a partial waiver of HIPAA Authorization for Screening/Recruitment. Pre-screening will include the following details:

- Received kidney transplant at the University of New Mexico
- Greater than 18 years of age
- Race/ethnicity details

PROTOCOL TITLE: **Improving Healthcare Outcomes in American Indian and Hispanic Transplant Recipients Using Culturally-Tailored Novel Technology (IMPACT)**

26. Documentation of Consent

A copy of the signed/dated ICF will be given to the subject. A copy of the signed/dated consent will be placed in the subject's research file that will be kept in a locked file cabinet. To document our consenting process we will be following the UNM HSC HRPO procedure titled, "SOP: Written Documentation of Consent (HRP-091)."

27. Study Test Results/Incidental Findings

NA

28. Sharing Study Progress or Results with Subjects

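### Adverse events enter the study only as staff learn of them, so detection is likely to differ by arm in months 0-6 and late events may go unrecorded in both arms

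*Combined protocol and SAP*

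**What the plan says.** Section 18 (Risks to Subjects) of the combined protocol and SAP states: "We expect the risks associated with the diet and exercise intervention to be minimal". The reason it gives is that "the licensed dietitian and physical therapist on the research team will closely monitor the patient participants, to minimize risk". It attaches no frequency to that monitoring.

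Section 12 (Study Procedures) sets the contacts:

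- IMPACT participants "will see the dietitian interventionist at every post-transplant appointment through six months post-transplant, with follow-up at 12 months post-txp". The visits follow the clinic schedule: weekly in month 1, fortnightly in months 2-3, monthly in months 4-6.
- For usual care: "They will only undergo the baseline interview, and a follow-up at 6 and 12-months post-transplant".
- Exercise can start after surgical clearance, usually 6-8 weeks after transplant. The later target activities are "movements that can be performed in the home without supervision", and the readable text gives no end date for them.
- Routine care continues for everyone: "in months 6-12, patients get labs every 1-2 months, and have a monthly clinic visit".

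Section 23 (Compensation) pays for "three visits for participants randomized to usual care and thirteen visits for participants randomized to IMPACT intervention".

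Under Section 14, unanticipated events go to the independent reviewer and the IRB within 24 hours of the study team learning of them. The principal investigator judges relationship to IMPACT. The independent reviewer looks at the data that the study has captured and may recommend stopping. Routine DSMB meetings are stated only until enrollment closes.

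The medical-record items listed in Section 12 are weight change, lipids, HbA1c, immunosuppression, BMI and other transplant-relevant history. Hospitalisations, falls and other adverse events are not named.

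**The concern.** When event capture depends on staff hearing about an event, the number recorded depends on how often staff and participant meet. One arm meets the study team at every clinic appointment for six months; the other is seen at baseline and then at month 6. An apparent excess of events in IMPACT could then partly reflect closer observation.

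After month 6 the problem changes. The arms have the same study visits, but there are none until month 12, while IMPACT participants may still be exercising at home unsupervised. The monitoring that Section 18 relies on is not visible in the visit schedule for that half of follow-up, and an event seen in clinic has no described path to the study team. At stake are the event counts by arm, the completeness of what the independent reviewer sees, and the safety information carried into the planned larger trial.

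**Working it through.** **1. Reproduce the visit counts.** Inputs are the clinic schedule and dietary text in Section 12 and the payments in Section 23.

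- IMPACT: 1 initial + 4 weekly + 4 fortnightly + 3 monthly + 1 at month 12 = 13, which matches the paid number.
- Usual care: baseline + month 6 + month 12 = 3, which also matches.
- Ratio of paid visits: 13/3 = 4.3.

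The usual-care paragraph of Section 12 gives 1-2 clinic visits a week in month 1. At two a week the IMPACT count would be 1 + 8 + 4 + 3 + 1 = 17, so the 13 rests on the once-weekly schedule.

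**2. Locate the difference.** Through month 6 IMPACT has 12 visits and usual care 2. From month 6 to month 12 each arm has one further visit, at month 12. Months 7-11 hold no described study visit and about 5 routine monthly clinic visits per participant in either arm. Visit-driven inequality can therefore arise only in months 0-6.

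**3. Illustrate coverage.** The protocol states no recall window, so this is a range. Assume that events are captured only at study visits, that each visit covers the preceding r months, and that baseline is at month 0.

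- IMPACT, months 0-6: visits to week 12 (12 × 12/52 = 2.77 months) are at most 0.46 month apart, so that period is fully covered for r of half a month or more. Three longer gaps to month 6 are each covered for r months. For r of 0.5 or 1 the share is (2.77 + 3r)/6.
- Usual care, months 0-6: r/6.
- Either arm, months 6-12: r/6.

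| Recall r | IMPACT, months 0-6 | Usual care, months 0-6 | Either arm, months 6-12 |
|---|---|---|---|
| 0.5 month | 4.27/6 = 0.71 | 0.08 | 0.08 |
| 1 month | 5.77/6 = 0.96 | 0.17 | 0.17 |
| 3 months | 1.00 | 0.50 | 0.50 |
| 6 months | 1.00 | 1.00 | 1.00 |

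If the usual-care baseline visit fell 6-8 weeks after transplant instead, one-month recall would cover (1 + 1)/6 = 0.33 of months 0-6. The gap narrows but remains.

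**4. Oversight after month 6.** Assume uniform enrollment over the 12-month recruitment period, at about the time of transplant. A participant enrolled at month e has max(0, 6 - e) months of late follow-up before enrollment closes. The average is (6 × 6/2)/12 = 1.5 of 6 months, or 25%. So about 75% of month 6-12 person-time falls after routine DSMB meetings stop. For all follow-up, the average before closure is 6 of 12 months, so 50% falls after.

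**5. Exercise exposure.** If home exercise continues to week 52 (assumption), exposure lasts 44-46 weeks. About 26 of those weeks follow the month-6 visit: 26/46 = 57% to 26/44 = 59%. This is time without a study visit, not time without clinical observation.

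**The case against.** The strongest reply is that these patients are well observed. All attend clinic monthly in months 6-12 at a single centre, and the study reads their records. Sections 2 and 3 describe close working between interventionists and the transplant team. Section 12 has the coordinator log observations and take feedback from that team. Twistle is meant to reach participants between appointments and to raise triage alerts. All of this stands, and it limits the late point to events that may be missed. A reader might infer that harms after month 6 will be missed; the documents do not support that. They do lack a procedure that turns a clinic finding into a study safety record.

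Three other strong readings also fail:

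- That the gap in months 7-11 causes unequal detection. The visit gap is the same in both arms.
- That three usual-care visits undercut the minimal-risk statement. That statement concerns risks of the diet and exercise intervention, which usual care does not receive.
- That 13 to 3 is a detection ratio. It counts paid visits. Section 12 also mentions four activity-monitor time points in either arm, so usual care may have one more contact, which sits uneasily with the three assessments stated there.

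It is also fair to say that the independent reviewer's criterion is danger to patients, not an arm difference, and that no adverse-event comparison is planned. With about 7-10 per arm, counts say little even under equal surveillance: zero events gives a one-sided 95% upper bound of 1 - 0.05^(1/7) = 35% or 1 - 0.05^(1/10) = 26%. The visit imbalance therefore does not show that a stopping judgement would be wrong. It does mean that the reviewer sees only what is captured, and captures it more readily in one arm early on.

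Figure 2, the appendices (including the Twistle script) and the operations manual are not available. Twistle contact or health prompts in months 7-11 cannot be ruled out.

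**Conclusion.** The concern holds in a limited form. Detection is likely to be unequal in months 0-6, when IMPACT has 12 study visits against 2. From month 6 to month 12 the two arms share the same weakness: no described study visit until month 12, and no stated route from clinic to study safety data. About 75% of that late person-time follows the end of routine DSMB meetings, under uniform enrollment. The coverage shares are illustrations that depend on the recall period and on capture only at study visits; with six-month recall the difference disappears.

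The consequence is confined to event counts by arm and to what reaches the independent reviewer. The acceptability and feasibility endpoints are unaffected. The Section 18 wording is not shown to be false, but the readable schedule does not bear it out after month 6.

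**What to change.** In Sections 12 and 14:

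1. Name a fixed list of events, for example hospitalisations, emergency visits, falls, injuries and graft events. Abstract them from the medical record on the same calendar in both arms through month 12, using the clinic visits that already occur.
2. Base any by-arm event summary on that common source. List events found only at IMPACT visits or through Twistle separately.
3. Do not send Twistle messages to usual care for this purpose. Twistle is part of what is being tested, so they would give controls some of the intervention's contact.
4. State how the independent reviewer receives safety data after enrollment closes.

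In Section 18, reconcile the monitoring statement with the visit schedule after month 6. In Section 12, reconcile the two first-month clinic frequencies, and the four activity-monitor time points with the three usual-care assessments.

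The cost is modest coordinator time for chart abstraction on 14-20 patients whose records the study already reads. No new visits or staff are needed.
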